Efficacy of Kinesio Taping in Musculoskeletal Neck Pain in Short and Medium Term. A Randomized Control Double Blinded Clinical Trial

TITLE: Efficacy of Kinesio Taping in Musculoskeletal Neck Pain in Short and Medium Term. A Randomized Control Double Blinded Clinical Trial

INVESTIGATOR PRINCIPAL: [name]

PROJECT ENTITIES: COMPLUTENSE UNIVERSITY OF MADRID & NURSERY, PHYSIOTHERAPY AND PODIATRY FACULTY.

NUMBER OF IDENTIFICATION:

DATE: 1ST JUNE 2021.

STUDY PROTOCOL

Type of Study: A double-blind controlled clinical trial was conducted with 30 days following.

Target population: Population with musculoskeletal neck pain.

Sample: A convenience sampling will be carried out among the patients according to eligibility criteria.

Inclusion criteria:

- Age between 18 and 30 years old,
- Presence of myofascial pain syndrome (MPS) and myofascial trigger point (MTP) in the upper trapezius muscle, according to the diagnostic criteria proposed by the American Academy of Pain Medicine and the scientific community a) tender point on palpation, with or without referred pain b) patient recognizes pain during tender point palpation c) at least three of the following: muscle stiffness or muscle spasm, limited range of motion in an associated joint, increase of pain with stress, palpation of tight band and / or nodule, associated with a tender point

- Understand written Spanish.

Exclusion Criteria:

- Neck pain of traumatic origin, due to recent surgery or causing radiculopathy.
- Have been diagnosed with chronic pathology, as well as neoplastic or suspicion of it.
- Have received some type of pharmacological or non-pharmacological analgesic treatment in the last 30 days
- Pregnant or menstrual women.

Sample size

The required sample size was calculated using the G * Power software (G * Power version 3.1.9.6). To identify the differences between the 3 intervention groups at the 3 evaluation moments, the sample size was estimated based on finding a moderate effect size (Cohen's $f = 0.25$). Considering an alpha error of 5% (0.05) and a beta error of 10% (statistical power of 0.9), he estimated the need for a sample size of at least 45 patients in total.

Procedure

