Efficacy of Kinesio Taping in Musculoskeletal Neck Pain in Short and Medium Term. A Randomized Control Double Blinded Clinical Trial

TITLE: Efficacy of Kinesio Taping in Musculoskeletal Neck Pain in Short and Medium Term. A Randomized Control Double Blinded Clinical Trial

INVESTIGATOR PRINCIPAL: [name]

PROJECT ENTITIES: COMPLUTENSE UNIVERSITY OF MADRID & NURSERY, PHYSIOTHERAPY AND PODIATRY FACULTY.

NUMBER OF IDENTIFICATION:

DATE: 1ST JUNE 2021.

Statistical Analysis Plan

The statistical software IBM SPSS® (Statistical Package for the Social Sciences 22, SPSS Inc., Chicago, IL USA) was used. The quantitative variables were presented as mean \pm standard deviation (SD), while the qualitative variables were shown as an absolute value (relative frequency percentage). To study the effects produced on the main variables of each intervention at different times of evaluation, an analysis of variance of repeated measures (factorial ANOVA) was applied. Secondarily, the same analysis was performed for each intervention on the secondary variable.

Additionally, the effect size (partial eta squared, η^2) was calculated for the changes produced by comparing within the same intervention group (intragroup) and comparing between intervention groups (intergroup), following the classification criteria described by Cohen: small (0.1 - 0.24), moderate (0.25 - 0.39), and large (> 0.4)

The interpretation of the statistical tests was performed based on a significance level of 5% ($p < 0.05$) for a 95% confidence interval.

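### The SAP grades partial eta squared with cut-offs that match Cohen's f, so effects are labelled smaller than the protocol's own use of 'moderate'

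*SAP*

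**What the plan says.** The effect-size paragraph of the SAP names its measure as "the effect size (partial eta squared"), to be calculated for changes "comparing within the same intervention group (intragroup) and comparing between intervention groups (intergroup"). It then grades the result, "following the classification criteria described by Cohen: small (0.1 - 0.24), moderate (0.25 - 0.39), and large (> 0.4"). It mentions no other effect-size measure and gives no conversion.

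The Sample size section of the protocol also uses 0.25 for a moderate effect, but on a different measure: "the sample size was estimated based on finding a moderate effect size (Cohen's $f = 0.25"). The aim there is "To identify the differences between the 3 intervention groups at the 3 evaluation moments". The remaining inputs are "Considering an alpha error of 5% (0.05) and a beta error of 10% (statistical power of 0.9"), leading to "he estimated the need for a sample size of at least 45 patients in total". The G*Power version is given. The effect-size option and the correlation between repeated measures are not.

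**The concern.** Partial eta squared is a proportion of variance. Cohen's f is the square root of a ratio of variances. One number cannot mark a moderate effect on both, yet 0.25 does so here. The SAP credits its bands to Cohen, and the only measure of his that either document names is f. The natural reading is that f cut-offs were carried over to partial eta squared without conversion.

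Because f²/(1 + f²) is smaller than f for every positive f, direct conversion always moves labels downward. These bands are the SAP's only rule for describing the size of an effect, and they cover both within-group and between-group comparisons. A result of the size the trial was planned to detect could be reported as 'small', or with no label, when the protocol calls it moderate.

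**Working it through.** **Inputs.** From the protocol: f = 0.25, alpha 0.05, power 0.90, k = 3 groups, m = 3 times, N = 45. From the SAP: cut-offs 0.1, 0.25 and 0.4 on partial eta squared (η²). Assumed: G*Power's default repeated-measures f, correlation ρ = 0.5 (range 0.3 to 0.7), sphericity, 15 patients per arm and no dropout.

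**1. The planned sample size.** For the group-by-time interaction, df1 = (k − 1)(m − 1) = 4, df2 = (N − k)(m − 1), and λ = f²·N·m/(1 − ρ). At N = 45 and ρ = 0.5, λ = 0.0625 × 45 × 3/0.5 = 16.875 with df 4 and 84, and power is 0.911. The smallest balanced N reaching 0.90 is 45, so the stated figure reproduces. At ρ = 0.3 it would be 60 and at ρ = 0.7 it would be 30. With G*Power's 'as in SPSS' option it would be 129.

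**2. Direct conversion.** η² = f²/(1 + f²) and f = √(η²/(1 − η²)).

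| f | η² |
|---|---|
| 0.10 | 0.0099 |
| 0.25 | 0.0625/1.0625 = 0.0588 |
| 0.40 | 0.16/1.16 = 0.1379 |

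| SAP band on η² | the same band on f |
|---|---|
| small, 0.1 to 0.24 | 0.33 to 0.56 |
| moderate, 0.25 to 0.39 | 0.58 to 0.80 |
| large, above 0.4 | above 0.82 |

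For example, η² = 0.15 is f = √(0.15/0.85) = 0.42, which the SAP would print as 'small'.

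**3. The scale behind N = 45.** G*Power's default repeated-measures f does not convert directly. The population value for the interaction is η² = λ/(λ + N(m − 1)) = 16.875/(16.875 + 90) = 0.158 (0.118 at ρ = 0.3, 0.238 at ρ = 0.7). Using df2 = 84 in place of 90 gives 0.167. Both lie in the SAP's 'small' band. On this scale at ρ = 0.5, η²/(1 − η²) = 3f², so the SAP's cut-offs 0.1, 0.25 and 0.4 are f = 0.19, 0.33 and 0.47. The planned 0.25 is still below the SAP's 'moderate', but by less than step 2 suggests.

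**4. Which significant results would be called small.** η² = F·df1/(F·df1 + df2) at the 5% critical value:

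- interaction, df 4 and 84, F = 2.48: 9.92/93.92 = 0.106
- between groups, df 2 and 42, F = 3.22: 6.44/48.44 = 0.133
- within one arm of 15, df 2 and 28, F = 3.34: 6.68/34.68 = 0.193

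Significant results from these values up to 0.24 would be printed as 'small'.

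**5. Labels when the true default f is 0.25.** These come from the noncentral F distribution. λ is 16.875 for the interaction, 0.0625 × 15 × 3/0.5 = 5.625 within one arm, and 0.0625 × 45 × 3/(1 + 2 × 0.5) = 4.22 for the group main effect.

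| Comparison | no label | small | moderate | large | below moderate at ρ = 0.5 (0.3; 0.7) |
|---|---|---|---|---|---|
| Interaction | 0.07 | 0.71 | 0.21 | 0.004 | 78% (91%; 39%) |
| Within one arm | 0.20 | 0.47 | 0.27 | 0.06 | 67% (77%; 43%) |
| Between groups | 0.44 | 0.47 | 0.08 | 0.004 | 91% (88%; 94%) |

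**The case against.** The strongest reply is that little depends on this. Effect size is an additional item in the SAP, inference rests on p < 0.05, and a reader who sees the partial eta squared can regrade it. That is right about the consequence, and it is why the point is one of wording only. It does not excuse a stated rule that gives the wrong label when followed.

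Second, the documents tie only 0.25 to f. That 0.1 and 0.4 are also f values is an inference, and the SAP does not rule out converting before grading. This is fair, but the conflict stands on 0.25 alone. The SAP names partial eta squared and then gives the bands, with no intermediate step.

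Third, the probabilities depend on unstated choices: the G*Power option, the correlation, 15 per arm, no dropout, sphericity, and how the within-group and between-group comparisons are run. This stands. They are illustrations, and the interaction figure runs from 91% to 39%. At correlation 0.7 the planned effect is 0.238 or 0.251 depending on the denominator, either side of the SAP's 'moderate' cut-off. That correlation does not reproduce N = 45.

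Fourth, converted bands push labels up. At correlation 0.5 the planned interaction would be called 'large' in about 79% of trials. With no true effect in one arm of 15, a label of 'moderate' or better would rise from 1.8% under the SAP's bands to 43%. This also stands, and it limits how the new labels may be used.

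**Conclusion.** The concern holds. The grading rule is wrong as written, because the protocol's 'moderate' is 0.25 on f and the SAP's is 0.25 on partial eta squared, with nothing linking them. No assumption is needed for that.

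The size of the shift does depend on assumptions. By direct conversion, a moderate f of 0.25 (0.059) gets no label and an f of 0.40 (0.138) is called 'small'. On the assumed planning scale, the planned effect (0.158) falls one grade, to 'small'. The error should be corrected, but it is confined to how results are described.

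**What to change.** Before results are seen, replace the grading sentence in the SAP with, for example: *Partial eta squared will be reported as a number with its p-value, and classified as negligible (<0.010), small (0.010 to <0.059), moderate (0.059 to <0.138) or large (0.138 or more), from eta squared = f²/(1 + f²) at f = 0.10, 0.25 and 0.40.* Alternatively, compute f = √(η²/(1 − η²)) and apply 0.10, 0.25 and 0.40 to f. Either form also closes the small gaps in the current bands, which leave values below 0.1, between 0.24 and 0.25, and between 0.39 and 0.4 without a label.

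In the protocol's Sample size section, state the G*Power effect-size option and the correlation. If the default option was used, add that the planning f is not on the scale of these bands. The new bands alone do not align the two documents.

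The cost is one sentence in each document, with no added patients and no changed test. The downside is that labels move upward: the planned interaction would be 'large' in 79% of trials at correlation 0.5 (59% at 0.3, 97% at 0.7). With no true effect, partial eta squared would still reach 0.059 in 27% of trials for the interaction and 43% for one arm of 15. A label should therefore never appear without its number and p-value, and the change should be dated. If the sponsor prefers, reporting partial eta squared without labels also removes the error.

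### The SAP tests two or more unnamed main variables at 5%, with no adjustment or testing order stated, and does not say which variable or ANOVA term decides efficacy

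*SAP*

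**What the plan says.** The Statistical Analysis Plan gives the purpose of the main analysis as "To study the effects produced on the main variables of each intervention at different times of evaluation", and the method is that "an analysis of variance of repeated measures (factorial ANOVA) was applied". It continues: "Secondarily, the same analysis was performed for each intervention on the secondary variable". Effect sizes are reported by "comparing within the same intervention group (intragroup) and comparing between intervention groups (intergroup"), with neither kind given priority. The error level is a single statement: "The interpretation of the statistical tests was performed based on a significance level of 5" per cent.

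The numbers of arms and visits come from the protocol, section Sample size, which sets the aim as follows: "To identify the differences between the 3 intervention groups at the 3 evaluation moments". The effect size is Cohen's f = 0.25. The error rates are given as "Considering an alpha error of 5% (0.05) and a beta error of 10% (statistical power of 0.9"), and the result is that "he estimated the need for a sample size of at least 45 patients in total".

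The only ranking in either document is main before secondary. Neither document lists the main variables, names a deciding ANOVA term or time point, states an adjustment or testing order, or says whether success is needed on one main variable or on all. No redaction or broken text at these points explains the silence.

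**The concern.** A factorial repeated-measures ANOVA with three arms and three visits gives three F tests per variable: arm, time and arm-by-time. With at least two main variables, there are at least four tests that could be read as evidence of a difference between arms (arm and arm-by-time for each variable). All are read at 5%, and nothing says in advance which one counts. If any one of them may carry the claim, the chance of a false claim exceeds 5%, and the deciding result can be chosen after the data are seen.

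A secondary point concerns time and within-arm effects. The SAP does not rank them below the between-arm result. They can appear when every arm improves alike, so they cannot show that taping works.

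**Working it through.** **Inputs from the documents.** Alpha 0.05 (SAP; protocol, Sample size). Power 0.90, f = 0.25, k = 3 arms, m = 3 evaluations, N = 45 (protocol, Sample size). Visits fall at days 0, 4 and 34 (protocol, Procedure: 4 days, then 30 more).

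**Assumptions.** Equal arms of 15; correlation over time ρ = 0.3, 0.5 or 0.7; sphericity (ε = 1) unless stated; 2 or 3 main variables; correlation between variables 0 to 0.7; no dropout. The documents give none of these.

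**1. Reproducing N = 45.** For the interaction, λ = f²·N·m·ε/(1 − ρ), with df (k − 1)(m − 1)ε and (N − k)(m − 1)ε.

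- At ρ = 0.5, ε = 1, N = 45: λ = 0.0625 × 45 × 3/0.5 = 16.875, df 4 and 84, power 0.911.
- At N = 42: λ = 15.75, df 4 and 78, power 0.887. So 45 is the smallest equal-arm total that reaches 0.90.
- At N = 45 with other correlations: 0.779 (ρ = 0.3) and 0.993 (ρ = 0.7).
- At N = 45, ρ = 0.5, ε = 0.75: 0.837.

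The match does not identify the interaction as the intended term. The time effect at ρ = 0.5, ε = 0.75 (λ = 12.656, df 1.5 and 63) also has power 0.911 at N = 45, and so also first reaches 0.90 there in equal arms. The interaction at ρ = 0.7, ε = 0.5 does the same (0.910).

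**2. False-positive chance if any one result suffices.** For q independent tests it is 1 − 0.95^q. Correlated variables were simulated under no arm difference (40,000 trials per setting, 3 × 15, ρ = 0.5).

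| Tests that may count | Main variables | Independent, exact | Simulated, correlation 0.7 |
|---|---|---|---|
| Interaction only | 2 | 1 − 0.95² = 0.0975 | 0.085 |
| Interaction only | 3 | 1 − 0.95³ = 0.143 | 0.115 |
| Arm or interaction | 1 | 1 − 0.95² = 0.0975 | not applicable |
| Arm or interaction | 2 | 1 − 0.95⁴ = 0.185 | 0.159 |
| Arm or interaction | 3 | 1 − 0.95⁶ = 0.265 | 0.213 |

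With one variable and one term the simulated rate is 0.050, as it should be.

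**3. If all main variables must succeed.** Alpha is not inflated, but power falls. With the same effect in each variable and ρ = 0.5, independent variables give about 0.911² = 0.83 (2 variables) and 0.911³ = 0.76 (3). Simulation over correlations 0 to 0.7 gives 0.83–0.86 and 0.75–0.82.

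**4. If alpha is split by Bonferroni, N = 45.** With 2 variables (alpha 0.025), power per variable is 0.683 / 0.854 / 0.984 at ρ = 0.3 / 0.5 / 0.7. With 3 (alpha 0.0167), it is 0.625 / 0.814 / 0.977. Restoring 0.90 per variable at ρ = 0.5 needs N = 51 with 2 variables (0.905) and 57 with 3 (0.919; 54 gives 0.8996).

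**5. Interaction first, then Holm-adjusted pairs, one variable.** If one arm shifts by d SD at both follow-ups, the interaction effect is f = d·√((2/3)(2/3)/9) = 2d/9, so f = 0.25 means d = 1.125. Simulated power at ρ = 0.3 / 0.5 / 0.7:

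- interaction alone: 0.777 / 0.912 / 0.992;
- interaction plus at least one true Holm-adjusted pair: 0.723 / 0.878 / 0.987.

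False rejection between the two equal arms is 0.026 / 0.029 / 0.039 with Holm, against 0.087 / 0.089 / 0.092 if the pairs are not adjusted after the gate.

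**6. Secondary point, time term.** If all arms recover equally by an assumed 0.25–0.5 SD, the time term is significant in 28% (0.25 SD, ρ = 0.3) to 99.6% (0.5 SD, ρ = 0.7) of trials, while the interaction stays at 0.048–0.051.

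**The case against.** The strongest reply is that the target can be inferred. The protocol sizes the trial on differences between groups across the visits, which fits an arm-by-time interaction, and N = 45 can be obtained from that term. This stands as a hint. It is not a decision rule, the arithmetic is not unique to the term (step 1), and even if the interaction is granted, the deciding variable stays open.

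A second reply is that a 5% threshold is compatible with adjusted p-values or with an all-must-succeed rule. That is correct. A reader might infer that the SAP commits to unadjusted testing, but it is only silent on adjustment. The inflation is therefore conditional on the success rule, which the SAP does not state.

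Third, the plural supports only two or more main variables, so every inflation figure rests on an assumed count. That also stands.

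Fourth, a reader might infer that the SAP means to read time or within-arm change as efficacy. It does not say so: within-arm comparison appears only in the effect-size sentence, and the trial is sized on differences between groups. The figures in step 6 show a possible misreading that the SAP does not rule out, and no more.

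Finally, applying the same analysis for each intervention could mean separate within-arm analyses. The factorial label favours one model with all arms, and the working assumes that. The ambiguity is another reason to name the model and the term.

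**Conclusion.** The point holds and should be acted on. Confidence is high that the deciding variable, deciding term, success rule and multiplicity approach are all unstated. The size of the consequence is conditional: about 8–10% (2 variables) or 11–14% (3) in place of 5% if any one interaction suffices, and about 16–19% or 21–26% if the arm term may count too. If all main variables must succeed, the cost is in power instead. The lack of ranking for time and intragroup effects is a lesser part of the point.

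Two stronger readings should be resisted. The stated N is not shown to be wrong: 45 is consistent with one interaction test at an undivided 5%. Nor do the documents show that error inflation will occur, because they state no rule that produces it. The design is not invalid; what is undefined is the confirmatory claim.

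**What to change.** Before outcome data are examined, amend the SAP to:

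- name one primary variable and make its arm-by-time interaction the single confirmatory test at 5%;
- only if that is significant, compare the three arm pairs at the two follow-ups (change from baseline, 3 × 2 = 6 tests) with Holm adjustment;
- treat the other main variables and the secondary variable as exploratory, the arm main effect as supportive, and time and intragroup changes as descriptive;
- state the assumed correlation over time and how departures from sphericity will be handled, since the visits are unevenly spaced.

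This is one valid scheme among several. The sponsor could instead require all main variables to succeed, or split alpha across them. Either should be stated and power restated (steps 3 and 4).

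**Cost.** SAP wording and a dated amendment, with no extra visits and no change to N = 45 under the one-variable rule. Fewer results can be called significant. Power for the full rule is about 0.88 at ρ = 0.5, slightly below the planned 0.90, and about 0.72 at ρ = 0.3, if one arm differs by the assumed 1.125 SD at both follow-ups.

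**Timing.** Both documents are dated 1 June 2021, the protocol's Procedure section places recruitment in May to July 2021, and the SAP is written in the past tense. The amendment should be dated and should say whether any outcome data had been seen. If they had, the choice of variable and term should be labelled post hoc.
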